4. Determine the potential alterations in VO₂max, anaerobic threshold, jump force, acceleration, step speed, and race time in college athletes, following a 12-week exercise program aimed at correcting two foot structural types (high or low). This investigation will use Ergospirometry and a 3D motion kinematics assessment system to evaluate possible improvements in sports performance resulting from the exercise program.

Methodology:

Design and Sample: An observational study design was employed to assess the impact of foot structural types on postural stability, activity of core stabilizing muscles, maximum oxygen consumption (VO₂max), anaerobic threshold, and lower limb performance in male college athletes over 18 years old from the University of Magdalena, participating in various sports modalities such as rugby, soccer, basketball, volleyball, tennis, table tennis, karate, and cheerleading. For evaluating the effects of a corrective exercise program targeting high or low foot posture alterations on the same variables, an experimental design was used. Stratified random sampling was employed for convenience, and 35 participants with low medial arch, 32 with high arch, and 36 with neutral arch were selected for the observational studies. For the experimental studies, 33, 31, and 33 participants were selected, respectively, from a pool of 230 candidate athletes. G Power 3.1.9.7 software was used to determine the appropriate sample size, considering three independent groups, an alpha level set at 0.05, a power (1-β) of 0.80, and an effect size (f) of 0.40.

Foot Type Evaluation: The Foot Arch Index, which determines the medial arch height by measuring the ratio between the midfoot area and the total foot area (excluding toes), was used to evaluate the foot type. An index less than 0.21 indicated a high-arched foot, an index greater than 0.26 indicated a flat foot, and an index between 0.21 and 0.26 was considered a "neutral" arch. Participants' footprints were obtained using a washable ink pad, and analysis software was used to calculate the Foot Arch Index.

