The measurements were performed during the general preparation stage of each sports semester, with no changes in diet and approximately two hours after the main meal of the day. To evaluate aerobic capacity (VO₂max) and anaerobic threshold, participants underwent an incremental treadmill test. The test began with a 3-minute warm-up at a speed of 4.8 km/h, increasing 1.2 km/h every minute while maintaining a constant 3% incline. Then, the main test started at 8.2 km/h with a constant 3% incline, and speed increased by 1.2 km/h every two minutes until exhaustion. The V-Slope method was used to measure VO₂ values at the anaerobic threshold. VO₂max was estimated based on three criteria: when the participant could not continue the test, when the VCO₂/VO₂ ratio exceeded 1.1, or when the maximum heart rate was reached with no more than a 10 beats/minute difference. To measure performance capacity, the countermovement jump (CMJ) technique was used, which involved jumping from a kneeling and hip-flexed position. Different parameters, such as maximum force, maximum velocity, maximum power, and level of developed force, were recorded. To assess lower limb speed and acceleration, the 40-meter linear acceleration test was employed, which demonstrated good reliability and validity.

Program of Corrective Foot Posture Exercises: In the experimental studies, the intervention group followed a 12-week exercise program aimed at correcting foot posture alterations, while the control group performed flexibility exercises. The exercises for the intervention group varied based on foot structural type (high or low) and focused on strengthening intrinsic and extrinsic foot muscles. The program was conducted under the supervision of an experienced physiotherapist. For participants with flat feet, exercises focused on strengthening the abductor hallucis, flexor digitorum brevis, and quadratus plantae muscles, with a progressive load over eight weeks. Additionally, myofascial release of the lateral long fibular muscle was performed. For participants with high arches, exercises emphasized improving flexibility of the tibialis posterior and gastrosoleus muscles. Strengthening exercises for the same muscles as in the flat feet group were also performed, with a gradual increase in load.

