Statistical Analysis: Data were reported as mean \pm standard deviation and analyzed using IBM SPSS Statistics (version 21, IBM Corp., NY, USA). The normality of each variable for different foot types (low, high, or neutral) was checked using the Shapiro-Wilk test. The significance of variables such as age, weight, height, and muscle/fat percentages among the three foot types was evaluated using ANOVA if the variables followed a normal distribution, or the Kruskal-Wallis test if they did not. For descriptive studies, ANOVA was used for normally distributed dependent variables or Kruskal-Wallis for non-normally distributed variables. Levene's test was used to assess homogeneity of variances. Post-hoc analysis with Bonferroni correction was performed to determine differences between groups. Pearson's or Spearman's correlation was used to assess the relationship between variables. For experimental studies, the effects of exercise on dependent variables were assessed using repeated-measures ANOVA or Friedman's test. Levene's test was used for variance homogeneity. Post-hoc analysis with Tukey correction was conducted to assess pre-post exercise significances of dependent variables. Eta-squared (η^2_p) or Kendall's W concordance coefficient was used to evaluate the effect size of the exercise program on foot types. The significance level for both studies was set at $p \leq 0.05$.

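### The program effect has no named program-versus-control test and no pre-test adjustment; if the arms were formed at random, adjusting for the pre-test would be more precise

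*Combined protocol and SAP*

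**What the plan says.** All references are to the Combined protocol and SAP.

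- **Statistical Analysis.** For the experimental studies, "the effects of exercise on dependent variables were assessed using repeated-measures ANOVA or Friedman's test". Then: "Post-hoc analysis with Tukey correction was conducted to assess pre-post exercise significances of dependent variables". Effect size is partial eta-squared or Kendall's W. No covariate, no between-group contrast and no confidence interval is named.
- **Program of Corrective Foot Posture Exercises.** There is a concurrent comparator: the intervention group follows the 12-week program "while the control group performed flexibility exercises". Corrective exercises are described for flat and high-arched feet only.
- **Design and Sample.** For the effect of the program "on the same variables, an experimental design was used". How athletes came to be in the program or the control group is not described. "Stratified random sampling was employed for convenience" concerns selection into the study, not allocation to an arm. Numbers are given by foot type only: "For the experimental studies, 33, 31, and 33 participants were selected, respectively, from a pool of 230 candidate athletes", in the order low, high, neutral. Arm sizes are not given, and neither is the role of the 33 neutral-arch athletes.

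**The concern.** Objectives 3 and 4 ask whether the program changes stability, core muscle activity and performance. With a control group available, the answer is the difference between program and control. The plan does not say which term of the repeated-measures ANOVA carries that difference, and its post-hoc tests look at change over time. A pre-post change can come from training during the season, from familiarity with the tests or from regression to the mean, none of which is an effect of the program.

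If the group-by-time term is what is meant, the test is valid in randomized arms, but it leaves information unused. It compares raw change scores, so a chance pre-test imbalance feeds into the estimate through regression to the mean. Using the pre-test as a covariate would remove that and reduce the variance. At stake are an interpretable estimate of the program effect and, if the arms are random, some precision in a study of 97 athletes.

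**Working it through.** **Inputs.** From the documents: two time points (pre and post); 33 low-arch, 31 high-arch and 33 neutral-arch athletes; alpha 0.05. Not in the documents: the pre-post correlation rho, the arm sizes and the allocation method. Rho is therefore taken over 0.3 to 0.9.

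**1. The plan's own figure.** The sample-size inputs (three independent groups, f = 0.40, alpha 0.05, power 0.80) give N = 66 in a one-way ANOVA (22 per group, power 0.818). The plan prints no calculated N. It selects 33 + 31 + 33 = 97, for which power at f = 0.40 is 0.944. This calculation compares three groups and uses neither arms nor rho, so it does not bear on the present point.

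**2. Which part of the plan compares program with control?**

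- Time main effect: average pre-post change over everyone. No.
- Group main effect: difference in the mean of pre and post. Not a difference in change.
- Tukey pre-post tests: change over time. No.
- Friedman's test: ranks each athlete's own two values. It has no arm term.
- Group-by-time: yes, but it is not named.

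**3. What group-by-time is with two time points.** It is the comparison of change scores between groups. On generated data with 64 v 33, the interaction F and the squared t on change were both 0.6042.

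**4. Precision in randomly formed arms.** With a common SD s before and after, variance per athlete is

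- change score: 2(1 − rho)s²
- ANCOVA: (1 − rho²)s²

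so the ratio is (1 − rho)(1 + rho) / [2(1 − rho)] = (1 + rho)/2. The extra athletes that the change score needs are 1/ratio − 1. If the change-score test had 80% power, ANCOVA would have Φ[(1.960 + 0.842)/√ratio − 1.960].

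| rho (assumed) | Change | ANCOVA | Ratio | Extra athletes | Power if change has 80% |
|---|---|---|---|---|---|
| 0.3 | 1.40 | 0.91 | 0.65 | 54% | 93.5% |
| 0.5 | 1.00 | 0.75 | 0.75 | 33% | 89.9% |
| 0.7 | 0.60 | 0.51 | 0.85 | 18% | 86.0% |
| 0.9 | 0.20 | 0.19 | 0.95 | 5% | 82.0% |

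Simulated standard errors (64 v 33, no baseline difference), change v ANCOVA, agree: 0.214 v 0.185 at rho 0.5, 0.168 v 0.156 at 0.7, 0.097 v 0.094 at 0.9.

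For scale, suppose one foot type were split 17 v 16 and the true difference were 0.5 SD (both assumed). By the normal approximation, power goes from 0.300 to 0.381 at rho 0.5, from 0.457 to 0.520 at 0.7, and from 0.894 to 0.909 at 0.9.

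**5. Arms not formed at random.** Suppose the groups differ by d before the program, the gap is stable and the program does nothing. The change score then expects d − d = 0. ANCOVA expects d − rho·d = d(1 − rho). With an assumed d of 0.5 SD that is 0.25, 0.15 and 0.05 SD at rho 0.5, 0.7 and 0.9. Simulation gave 0.256, 0.152 and 0.051 for ANCOVA and at most 0.006 for the change score.

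**6. Can an arm-by-foot-type model be fitted?** With three foot types, a model with arm, foot type, their interaction and pre-test has 1 + 1 + 2 + 2 + 1 = 7 columns. If all neutral athletes are controls and all others receive the program, arm is determined by foot type and the rank is 4. If low- and high-arch athletes are split and all neutrals are controls, one cell is empty and the rank is 6. The interaction can be estimated only among foot types that contain both arms.

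**The case against.** The strongest reply is that the plan never names group-by-time, so calling its analysis a change score picks one reading. That stands. The equivalence in step 3 holds for that reading only; under the others there is no program-versus-control comparison at all.

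Second, the precision gain presupposes random arms. A reader might infer from the experimental label and the mention of random sampling that ANCOVA is simply the better analysis here. The documents do not support that. They describe no allocation, count athletes only by foot type and give corrective exercises only for low and high arches, so neutral-arch controls are a plausible reading. On that reading step 5 applies, and ANCOVA may introduce a bias that the change contrast avoids. This also stands, and it makes the recommendation conditional. It also rules out treating the 33 low-arch and 33 neutral-arch athletes as two randomized arms for a power example.

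Third, the gain may be slight. The plan describes the 40-meter test as reliable and valid, and takes four static measurements and five jumps. If rho is near 0.9, only 5% of the variance is recovered. A reader might also infer that the planned confidence intervals are too wide, but none are planned.

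Finally, group-by-time is a valid test in randomized arms, so choosing ANCOVA over it is a matter of efficiency. That is right. What remains is that the plan leaves the between-group contrast unnamed.

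**Conclusion.** The point holds in a conditional form. The documents show that no program-versus-control contrast is named and that the pre-test is not used as a covariate. If group-by-time is intended, it is an unadjusted change-score comparison. ANCOVA would then have 0.65 to 0.95 of its variance, assuming random arms, equal pre and post SD, and rho between 0.3 and 0.9. If the arms were not random, that advantage cannot be claimed: an assumed stable 0.5 SD baseline gap would give a spurious ANCOVA effect of about 0.25 SD at rho 0.5. The change contrast is unbiased there only if the groups would have changed equally without the program. The plan should be amended, but which analysis should be primary depends on how the arms were formed.

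**What to change.** 1. State how the program and control arms were formed, how many athletes of each foot type are in each, and what the neutral-arch athletes do.
2. For each outcome, make one program-minus-control difference with its 95% confidence interval the test of the program effect, in place of pre-post tests within groups or Friedman's test.
3. If arms were randomly formed within the low- and high-arch groups, regress the post-test on arm, foot type and pre-test among those athletes. Add arm-by-foot-type only where both arms exist in each foot type. Report the change-score result as sensitivity.
4. If arms were not random, for example if neutral-arch athletes are the controls, keep the between-group change contrast (group-by-time) as primary and show ANCOVA only as sensitivity.

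The cost is a clarification of the design, revised analysis wording, one degree of freedom per outcome and a check that the pre-test slopes are parallel. No new measurements are needed.

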Structural Types of the Foot and Their Influence on Core and Sports Performance in College
Athletes

NCT ID not yet assigned

Date: 25/August/2022

Structural Types of the Foot and Their Influence on Core and Sports Performance in College Athletes

General Objective:

The objective of this study is to assess the impact of foot arch height and the implementation of a corrective exercise program on foot posture alterations in college athletes. The evaluation will focus on three aspects: postural stability, muscular activity at the center of gravity, and sports performance. This assessment will be conducted using advanced measurement systems such as Surface Electromyography, motion analysis technology, Ergospirometry, and body motion kinematics measurement systems. The findings of this study aim to contribute to the optimization of athlete training and overall performance.

Specific Objectives:

1. Compare the average muscular activity at the center of gravity and both static and dynamic stability among college athletes with low, high, and neutral foot arches. This analysis will employ Surface Electromyography and a 3D motion measurement system. The goal is to determine the potential influence of different foot structural types on core muscle activity and overall stability in athletes.
2. Assess the potential variations in jump force, acceleration, step speed, race time, maximum oxygen consumption, and anaerobic threshold among college athletes with high, low, or neutral foot arches. This investigation will utilize biomechanical analysis technology and Ergospirometry, with the aim of identifying any possible impact of varying foot structural types on athletes' performance capacity.
3. Evaluate the potential changes in terms of center of gravity muscle activity and both static and dynamic stability after a 12-week exercise program designed to correct different foot structural types (high or low) in college athletes. This assessment will employ Surface Electromyography and a 3D motion measurement system, with the objective of establishing the effectiveness of these exercises in improving athletes' body stability.

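### Tukey is the correction named for two-level pre-post comparisons, where it adds no adjustment or answers another question, and the named follow-up does not use the control group

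*Combined protocol and SAP*

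**What the plan says.** Specific Objectives 3 and 4 concern change in stability, core muscle activity and performance; Objective 3 words it as change "after a 12-week exercise program designed to correct different foot structural types (high or low) in college athletes". No intermediate assessment is described, so time has two levels.

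Under Design and Sample: "For the experimental studies, 33, 31, and 33 participants were selected, respectively, from a pool of 230 candidate athletes". In the order given there, these are 33 low-arch, 31 high-arch and 33 neutral-arch athletes, 97 in all. The section on the corrective exercise program describes an intervention group, "while the control group performed flexibility exercises". Neither section says which foot types the control athletes come from.

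Under Statistical Analysis, "the effects of exercise on dependent variables were assessed using repeated-measures ANOVA or Friedman's test", followed by "Post-hoc analysis with Tukey correction was conducted to assess pre-post exercise significances of dependent variables". The section does not say which means form the Tukey family or which error term is used, and it names no follow-up suited to Friedman's test. Bonferroni is named only for group differences in the descriptive studies. "The significance level for both studies was set at" 0.05.

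**The concern.** Tukey's procedure controls error over all pairs among several means. A before-after comparison in one group is a single pair of correlated means, so the named correction does not fit the named comparison. The analyst must then choose among several ways of running it, and these differ widely in error rate and power. A reader of the results could not tell which was used.

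There is a second gap. The experiment has a control group, but the only follow-up named concerns pre-post change. A significant change within an intervened group does not separate the program from ordinary training or the passage of time. This is the only follow-up test named for Objectives 3 and 4.

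**Working it through.** **Inputs from the document.** Groups of 33, 31 and 33; two time points; alpha 0.05.

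**Assumed, because the document gives no values.** Unit SD at both times; a change of 0.5 SD; pre-post correlation r = 0.7, with 0.5 to 0.9 as the range.

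**1. The plan's own figure.** The sample size was set "considering three independent groups, an alpha level set at 0.05, a power (1-β) of 0.80, and an effect size (f) of 0.40". With λ = N·f², N = 66 gives λ = 66 × 0.16 = 10.56 and power 0.818; N = 97 gives 0.944. The plan prints no required N to compare with. This calculation concerns three independent groups and does not bear on pre-post change.

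**2. Tukey on the two time points.** The cutoff on the t scale is q(0.95; k, df)/√2. For k = 2 it is 2.0369 at 32 df, and t(0.975; 32) is also 2.0369. The two also agree at 30 df (2.0423) and 94 df (1.9855). No adjustment is made. Over three groups the error is 1 − 0.95³ = 0.143 (0.136 to 0.147 in simulation). Bonferroni over three would give 1 − (1 − 0.05/3)³ = 0.049.

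**3. Tukey on foot type.** Each athlete contributes (pre + post)/2. If every group gains δ, every group mean rises by δ/2 and the differences between groups do not move. In simulation with an equal 0.4 SD gain in all groups, some pair is significant in 4.9% of runs at each of r = 0.5, 0.7 and 0.9. That is the test's alpha level. With a 0.5 SD gain in low and high arches only, the figure is 17% to 20%.

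**4. Tukey on six cells treated as independent.**
- Cutoff: q(0.95; 6, 188)/√2 = 2.879, with 188 = 2 × 97 − 6.
- Standard error used: √(2/33) = 0.246, so a change must exceed 2.879 × 0.246 = 0.709 SD.
- Actual standard error of a mean change: √(2 × 0.3)/√33 = 0.775/5.745 = 0.135.
- Power ≈ P(Z > (0.709 − 0.5)/0.135) = P(Z > 1.55) = 0.06 (0.07 in simulation).
- Unadjusted paired test: noncentrality 0.5/0.135 = 3.71 on 32 df, power 0.95.

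**5. Six-cell cutoff with the within-athlete error.** The cutoff is 2.909 at 94 df. With noncentrality 3.71, power is 0.78. Simulated familywise error for the three pre-post contrasts is 0.010 to 0.015. So, of the gap in step 4, the stricter cutoff takes power from 0.95 to 0.78, and loss of the pairing takes it from 0.78 to 0.06.

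**6. Contrast against control.** The standard error is 0.775 × √(1/n₁ + 1/n₂).

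| Sizes | SE | 0.5/SE | Power at 0.05 |
|---|---|---|---|
| 33 v 33 | 0.191 | 2.62 | 0.73 |
| 17 v 16 | 0.270 | 1.85 | 0.43 |

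The first row assumes neutral-arch athletes are the controls. The second assumes a group of 33 is split into intervention and control. Both are before any Holm adjustment.

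**The case against.** The strongest reply is that the sentence is loosely worded but workable. Repeated-measures ANOVA supplies the within-athlete error. Tukey on two levels with that error is a valid paired test in each group, only unadjusted; the six-cell version in step 5 keeps the pairing and controls error. This stands. A reader might infer that Tukey cannot test pre-post change at all, or that every way of running it fails. The document does not support that.

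A reader might also infer that baseline foot-type differences will almost always be reported as exercise effects. Simulated rejection under step 3 is 95% to 99% with no program effect, but only if baseline differences of f = 0.40 are assumed. The plan uses that value solely as a sample-size input. This reading also depends on which post-hoc options the software offers for a within-subject factor, which the document does not describe, and it conflicts with the sentence's stated aim of assessing pre-post change.

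Two points on size also stand. The 14% assumes ungated tests with every null true; if the follow-ups are run only after a significant omnibus result, the error in that same all-null case is about 3% to 7%, depending on the gate. The plan does not state a gate. And treating the cells as independent is the least natural reading of a repeated-measures plan.

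Finally, the omnibus tests of time and group-by-time, and partial eta-squared, do not depend on the Tukey sentence. That lowers the severity. It does not supply a contrast against control.

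**Conclusion.** The point holds as a faulty and under-specified follow-up method. Over two time points the stated correction corrects nothing, and three foot-type groups carry up to about 14% error per outcome if tested independently and ungated. The other simple readings either do not address change or discard the pairing (power about 6% against 95%, at an assumed 0.5 SD and r = 0.7). A valid, conservative version exists at power about 0.78, but the plan does not name it. Under any of these readings the follow-up is not a comparison with control.

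The cutoff equality in step 2 is exact and needs no assumption. The power figures rest on the assumed change and correlation. The sentence should be fixed before analysis; the omnibus repeated-measures ANOVA is unaffected, so the point does not invalidate the experimental analysis as a whole.

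**What to change.** - State in the protocol how control athletes map onto foot types: controls within each foot type, or neutral-arch athletes as the controls. The contrasts cannot be written until this is settled.
- Replace the Tukey sentence with the group-by-time contrast: pre-post change in intervention minus pre-post change in control, on the within-athlete error term, Holm-adjusted over the contrasts that the stated mapping yields.
- Report change within each group as a paired mean change with a 95% confidence interval.
- In the non-parametric branch, name a rank-based comparison of change scores between intervention and control.

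The cost is protocol and SAP wording and a few lines of analysis syntax; no new data are needed. The downside is power. At the same assumed effect and r = 0.7, the contrast against control has about 0.73 with 33 v 33 or 0.43 with 17 v 16, before adjustment, against 0.95 for a within-group paired test. The plan should acknowledge this loss, which is the price of answering the controlled question.

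### The program effect is summarised by an ambiguously named, unsigned index, and no program-minus-control difference in change with a confidence interval is planned

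*Combined protocol and SAP*

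**What the plan says.** In the combined protocol and SAP, the Statistical Analysis section states that "the effects of exercise on dependent variables were assessed using repeated-measures ANOVA or Friedman's test", and then that eta-squared, printed with the symbol η²p, or Kendall's W "concordance coefficient was used to evaluate the effect size of the exercise program on foot types". It does not say whether the effect size belongs to time, group or group x time. Apart from this index, it plans means with standard deviations, Tukey-corrected pre-post comparisons and a significance level of 0.05. It mentions no difference in change between groups and no confidence interval.

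The section on the corrective exercise program describes an intervention group and a control group that did flexibility exercises. Specific objective 3 evaluates the program "with the objective of establishing the effectiveness of these exercises in improving athletes' body stability", and objective 4 looks for improvement in sports performance.

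The sample size under Design and Sample was set "considering three independent groups", with "an alpha level set at 0.05, a power (1-β) of 0.80, and an effect size (f) of 0.40". On numbers it says: "For the experimental studies, 33, 31, and 33 participants were selected, respectively, from a pool of 230 candidate athletes". It does not say how these three foot-type groups map onto program and control.

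**The concern.** Effectiveness against a control is a signed quantity: how much more the program group changed than the control group, in which direction, and with what precision. Eta-squared, partial eta-squared and Kendall's W are all unsigned, so a gain and a loss of equal size give the same value.

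The label adds a second problem. In a pre-post analysis, plain eta-squared divides by the total variation, including that between athletes. Partial eta-squared leaves the between-athlete part out, so it grows as the two measurements become more correlated. The outcomes range from 10-second eyes-closed sway and surface EMG to VO₂max and a 40-metre sprint, and there is no reason to expect one common correlation. The same standardised change could then give quite different values for different outcomes. A reader who took the index as the size of benefit could be misled, and the report would still lack an interval for the contrast of interest.

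**Working it through.** **Inputs.** From Design and Sample: f = 0.40 and experimental groups of 33, 31 and 33. Assumed, because the documents give neither: the pre-post correlation rho, shown over a range, and equal pre and post SDs. The plan states no value of eta or W to reproduce.

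**Step 1: planning effect on the eta scale.** η² = f²/(1 + f²) = 0.16/1.16 = 0.138. This f is for independent groups. With three equal groups it means a spread between extreme group means of at least 0.40 × 6/√8 = 0.85 SD.

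**Step 2: name against symbol.** Take a change of 0.2 SD in one group of n = 33.
- Plain eta-squared: (δ²/4)/(δ²/4 + 1) = 0.01/1.01 = 0.010 at every rho.
- Partial eta-squared: dz² = δ²/[2(1 − rho)] and η²p = n·dz²/(n·dz² + n − 1).
  - rho 0.5: dz² = 0.04; 1.32/33.32 = 0.040
  - rho 0.8: dz² = 0.10; 3.3/35.3 = 0.093
  - rho 0.9: dz² = 0.20; 6.6/38.6 = 0.171
  - rho 0.95: dz² = 0.40; 13.2/45.2 = 0.292

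The two readings of the label differ about 4-fold at rho 0.5 and 29-fold at rho 0.95.

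**Step 3: change that gives η²p = 0.138, by model term.** Let s = √[2(1 − rho)], the SD of change in units of the raw SD.
- One-group time effect, n = 33: dz² = 0.16 × 32/33 = 0.155, so δ = 0.394s.
- Group x time, two equal arms: f = (δ/2)/s, so δ = 0.80s.
- Group x time, three equal groups of which two change by δ and one by 0: f = (δ√2/3)/s, so δ = 0.849s.

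The last two are population values, without the small-sample factor used in the first.

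| rho | s | one-group time | two arms | three groups |
|---|---|---|---|---|
| 0.5 | 1.000 | 0.39 | 0.80 | 0.85 |
| 0.8 | 0.632 | 0.25 | 0.51 | 0.54 |
| 0.9 | 0.447 | 0.18 | 0.36 | 0.38 |
| 0.95 | 0.316 | 0.12 | 0.25 | 0.27 |

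**Step 4: when would 0.2 SD reach 0.138?** Using population values, solve 0.2 = c·s for rho, so rho = 1 − (0.2/c)²/2. With c = 0.40 (one group) rho = 0.875. With c = 0.80 (two arms) rho = 0.969. With c = 0.849 (three groups) rho = 0.972.

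**Step 5: sign and Kendall's W.** In 20,000 simulated samples of n = 33, changes of +0.2 and −0.2 SD gave the same mean η²p within simulation error. W for two time points averaged about 0.054, 0.090, 0.147 and 0.246 at rho 0.5, 0.8, 0.9 and 0.95. It too is unsigned and rises with rho.

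**Step 6: can an interval be recovered from the planned tables?** The variance of change is SD²pre + SD²post − 2·rho·SDpre·SDpost. Means and SDs give the raw change, but without rho they do not give its standard error.

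**The case against.** The strongest reply is that the index only supplements other reporting. Means and SDs in the outcome's own units are planned, with pre-post comparisons, so a reader will see direction and raw size. That stands: the lack of a sign is a property of eta and W, not of the whole report.

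The second reply is that the dependence on rho is conditional. If plain eta-squared was computed, as the word says, it does not arise. That also stands, and it is why the label has to be settled.

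A reader might infer more: that a trivial change will pass for the planning effect, or that outcomes will be ranked by their reliability. The documents support neither.
- They give no rho and no threshold for a trivial change.
- They never compare eta with f and never rank outcomes by it. Partial eta-squared depends on the change as well as on rho.
- For group x time, the term that compares program with control, a 0.2 SD change matches 0.138 only near rho 0.97. At rho 0.5 the matching change is 0.80-0.85 SD, which is not small.

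What the reply does not meet is the missing estimate: no between-group difference in change and no interval is planned, and the interval cannot be rebuilt from means and SDs.

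**Conclusion.** The point holds as a defect in how the program effect is estimated and reported. Three parts rest on the text alone: the name and symbol conflict, the model term is missing, and no signed program-minus-control difference in change with an interval is planned, although objectives 3 and 4 ask about improvement and a control group exists.

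The size of the distortion is conditional on partial eta-squared being meant and on an assumed rho. Between rho 0.5 and 0.9, the change that corresponds to one value, 0.138, falls from about 0.39 to 0.18 SD for a one-group time effect, and from about 0.80-0.85 to 0.36-0.38 SD for group x time. In each case it shrinks by a factor of about 2.2 (1.000/0.447), which is enough to make values non-comparable across outcomes of different reliability. It does not show that any particular result will mislead, or that the planned significance test is invalid. The change should be made because it determines what the trial can say about effectiveness.

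**What to change.** - Make the main reported effect for each outcome the program-minus-control difference in pre-post change, in the outcome's own units, with a 95% CI. Optionally give it divided by the pre-test SD as well.
- Base the statement of effectiveness on the sign and interval of that difference.
- State which athletes form the program and control groups within the 33, 31 and 33, so that the contrast is defined.
- Keep eta or Kendall's W only as secondary. Say whether eta is plain or partial and tie it to group x time.
- Do not compare these indices across outcomes or with the planning value "an effect size (f) of 0.40".

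The cost is slightly more analysis and table work. No new data are needed.
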